Exploratory Analysis: Patient and PHCP correlates of CVRS and changes in CVRS in RA; Change in PHCPs CVRA	CVRS and changes in CVRS, Change in CVRA for PHCPs	Modifiable patient and PHCP correlates of CVRS and changes in CVRS would be identified. PHCP CVRA is modifiable.	Predictors of CVRS or change in CVRS will allow evidence based development of targeted strategies for patient and PHCP to improve CVRS in RA for future. Improvement in CVRA in PHCP will help facilitate further studies, interventions, and PQRI incentives	

CVRA: Eighteen modifiable and non-modifiable traditional CVR being assessed are (a) Fifteen Non-modifiable and modifiable CVR: Age, Male gender, Postmenopausal status, Ethnicity, Family history of premature CVD (in father at age <55 yrs, or mother at age <65 years), smoking, dyslipidemia, hypertension, physical inactivity, obesity (>20% over ideal body weight), diabetes, stress, excessive alcohol, autoimmune diseases (e.g. RA), steroids, and (b) three RAspecific (Disease activity, duration, use of steroids).

CVRS: Checklist used to assess CVRS will include only primary CVR factors, and these will include elicitation of history of diabetes (if present, glycosylated hemoglobin annually in diabetics), dyslipidemia (if present, lipid panel in past one year), hypertension (if present, control of blood pressure in past one year), rheumatoid arthritis (Steroids, lipid panel in past one year), smoking (if present, education for cessation in past one year), poor activity level (if present, education on exercise in past one year), obesity (if present, BMI and/or weight loss education documentation in past one year), family history of CVD.

Data Collection: All consecutive patients with a diagnosis of RA seen in the Rheumatology clinics will be sought for participation. Inclusion criteria: A. *RA patients*: Adult men and women

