meeting the following criteria (i) Diagnosed with RA with following criteria: Inflammatory symmetric polyarthritis of \geq 6 weeks, with physician documented synovitis in medical records (past or current) consistent with RA, with or without rheumatoid factor, anti cyclic citrullinated peptide or radiologic evidence of RA. Exclusion of another etiology for above. (ii) Receipt of care by rheumatologist at either RUMC or JSH. This will allow us access to full medical records to correctly gauge the prevalence of CVRS. (iii) Informed consent. *B. PHCP*: (i) Physicians providing primary care to the RA patients recruited for this study for the El group. Definition of PHCP has been previously provided (section F), (ii) Informed consent (iii) Not providing PHCP to RA patients in the non-El group.

1.2. *Methods: 1.* Education intervention development phase: The primary outcome of the intervention development phase will be patient-centered EI video and PHCP-centered education EI to increase CVRA in RA. The interdisciplinary study team will develop a multi-level web-based EI for CVRA targeted to RA patients and their PHCPs. This team will consist of 3-6 RA patients and the panel of experts in rheumatology, preventive cardiology/endocrinology, and experimental health and social psychology. To improve overall RA patient outcomes, our educational approach for the web-based EI is specifically aimed at changing the knowledge, and thus health behaviors of RA patients and their PHCP.

Educational Approach: In the **development of the web-based EI** (Table 1, Figure 1), we will utilize credible, useful, innovative educational platform and input from opinion leaders in the therapeutic areas. All educational content will be learner centric in approach, language and content (Table 2). Content appropriateness of the tailored intervention will be verified by the health experts. Processes of change will be focused on increasing RA patients or their PHCP CVRA in general and in RA, and increasing their awareness of the need for change. This 20-30 minute You Tube EI video will be developed using scientifically researched content (Table 2).

	Table 2: Develo	opment of Content for Educational web-based Intervention
Audience	Major Areas in Content Develo	Key Features
Patients	1) What is CVD and CVD in USA	Definition of CVD, Leading cause of death
	2) CVD in Women	Leading cause of death in women

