2 will be paired data. Medical charts records will be reviewed to quantify prevalence of CVRS by PHCP (within one-year period preceding baseline visit) at baseline and one-year follow up visit. For patients whose PHCP is not within Rush University Medical Center or John H Stroger Hospital, we will contact their local PHCP to obtain their pertinent medical records to quantify prevalence of CVRS by PHCP (within one-year period preceding baseline visit) at baseline and one-year follow up visit. Study participants will be asked to provide informed consent to communicate with their PHCP and access to their medical records to allow for assessment of CVRS.

Assessment of CVRA in PHCPs: PHCPs will be contacted by email. Acceptance to proceed with the study online will be taken as informed consent. Online survey on their CVRA (*Baseline PHCP survey*) will be evaluated using case scenarios developed specifically for this purpose, followed by a You-Tube video developed using evidence based literature review, specially including autoimmune diseases and risk of CVD in women and RA. This will be developed at the level of the targeted audience and of 20-30 minutes duration. They will then be prompted to take the same case scenario based survey immediately to assess their CVRA (*Follow up PHCP survey 1*). An exit online credibility survey will be used to gather feedback on credibility (user-friendliness, content, understandability, and relevance), barriers experienced in using the webbased intervention and any suggestions (open-ended).

I.3.Tools:

IRB

Survey to assess CVRA: The survey will include the following components:

1. The content of Patient surveys: Brief survey to collect demographic and self reported past medical history, family history, Social history and current medications, current weight and height. This will be administered to RA.

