Rates for CVRS at baseline and one year later for all RA patients (with and without EI) will be determined using a checklist.

I.7. Proposed Analyses: (Table 1) SPSS software will be used for data analyses. Data distribution will be evaluated. Standard descriptive statistics will be used to analyze (a) patient characteristics: demographics, socioeconomic status, RA disease pertinent information; and (b) PHCP characteristics: demographics, type of physician and practice, board certification status, and annual count of RA patients. Comparison between demographics and disease characteristics of RA patients with and without EI will be conducted using chi square and t test analysis.

I. Intervention development phase

Aim 1. Qualitative analyses will be used to gather data about the content, relevance, ease-ofuse, credibility and delivery of the educational materials. This data will be used to refine the intervention. Descriptive EI fidelity monitoring data analysis will be undertaken (mean duration (Patient or PHCP) engagement YouTube EI video, completion of CVRA at follow up 1 for patients and PHCPs, and credibility survey data). Latter data will evaluate the need, ease, content and understandability, relevance of the EI.

Engagement of audience will be judged through observation of body language RA patients during the entire study. In addition, feedback on the credibility of the intervention is being sought from both the patients and PHCP to establish its user-friendliness, content, relevance and understandability. Moreover, special efforts have been undertaken to limit survey burden and limit the duration of the EI to allow for full engagement of the participants. We feel that the technology platform being used for the intervention, brevity, its speed and ease will allow for greater audience engagement.

II. Pilot-testing phase.

Aim 2A. To compare changes in CVRA in RA patients (a) after web-based EI. We hypothesize that 20% increase in overall CVRA (measured using standardized survey) at 2-3 months post intervention; (b) with and without web-based EI. We hypothesize significantly greater improvement in overall CVRA among RA patients with EI as compared to non EI group, at 2-3 months.

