For patients (a) Overall CVRA (ORA), (b) Traditional CVR awareness (TRA) (c) RA CVR awareness (RARA) will be calculated. Awareness of all 18 CVR being tested (listed in section 1) will denote 100% CVR awareness. To score ORA, patient's correct responses denoting awareness to each of the 18 CVR being tested will be calculated in percentage of total responses. Domain-specific CVR awareness for traditional CVR (TRA) and RA (RARA) will be scored separately using the same strategy.

CALL AND AND A

Paired t tests to compare pre and post (Follow up 2) patient overall CVRA for our primary outcome of interest will be performed. Effect size of gains in overall CVRA for RA patients after EI (Follow up survey 2 and baseline) will be calculated. We will then compare percent change in overall CVRA rates (between baseline and follow up 2) using chi square analysis, among EI and non-EI patients with RA. A p value of ≤ 0.05 will be considered significant on two tailed tests.

Aim 2B. To explore changes in cardiovascular risk screening (CVRS) at the primary health care visits among RA patients with and without EL.

The medical records of RA patients with and without EI will be reviewed in electronic medical record, and analyzed using standardized checklist to assess the prevalence of CVRS and CVD risk reduction plan (meaningful use). Changes in CVRS rates among EI and non EI groups will be calculated, and compared using chi square analysis. A p-value of ≤ 0.05 will be considered significant on two tailed tests.

Exploratory analysis on improvement in PHCP overall CVRA using analysis similar to those discussed for aim 2a will be undertaken, a post hoc power analysis and effect size will be obtained. In addition exploratory univariate and multivariate logistic or linear regression analysis for patient and PHCP correlates of CVRS (baseline) and change in CVRS will be performed. Improvements in Traditional and RA-specific CVRA among RA and PHCPs will be assessed.

J. Dissemination plan: The first step in disseminating outcomes will be to share the results of the study with the participants of the study, RA patients and their PHCP.

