Next, the results of the study would be submitted for presentation at a regional or National conference pertinent to primary care providers, rheumatology and preventive cardiology audience. Options include American College of Physicians, Quality improvement conferences, American College of Rheumatology, American Heart Association and Women's health Conferences. Preparation and publication of the manuscript will be the pivotal step in disseminating the outcomes. Potential target journals for submission could be from Internal Medicine, Preventive Medicine, Cardiovascular, Outcomes or Rheumatology based. General Medicine Journals targeted could include Journal of American Medical Association, Lancet,

while cardiology journal circulation may be of interest. Rheumatology journals of interest would include *Journal of Rheumatology, Arthritis Care and Research, Annals of Rheumatic Diseases* or *Arthritis Research & Therapy.* Publication of data may encourage discussion or statement from the National organizations with strategies to increase CVD risk awareness and screening. Continuing medical education activities could be built based on the results dissemination.

We feel that web-based EI could reach many more RA patients in a timely fashion without using many resources. In addition, this strategy could provide patients ease, flexibility and privacy with their educational module administration. National organizations such as the Arthritis Foundation and with support of such web-based resources through unrestricted educational funds could further mobilize this intervention to across the globe.

K. Project Timeline: Major study processes and data accrual with corresponding anticipated timeline are shown below in figure 1. Deliverables and timelines for entire project are shown in Table 5 below.

Table 5: Project Timeline and Deliverables			
Deliverable	Tasks	Date	
Institutional Review Board	Regulatory documents, HIPPA etc for RUMC and JSH	1/1/2015-3/1/2015	
Develop Study Documents	Defining processes, training of research assistant, study cordinator, incentives/parking organization	1/30/2015-3/1/2015	
CVR Surveys	Modify the existent survey tools, Obtain permission for use of surveys, Collaborative meetings to discuss content and format, Develop Case Scenarios for Physicians, Reviews, Refinement, Pretest surveys	3/1/2015 to 5/30/2015	

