You tube Educational module-Pat	Focus group, gather pertinent content, parse information, develop transcripts, assess understandibility level, schedule recording, recording, editing, pretesting, refining	6/30/2015	
You tube Educational module-Phy	Gather pertinent content, parse information, develop transcript, assess reading/understandibility level, schedule recording, recording, editing, pretesting, refining	6/30/2015	
RA and PHCP recruitment status	At RUMC and JSH	7/1/2015 to 7/1/2016	
Medical Chart reviews for RA patients Baseline	Identification of PHCP, review of records, data entry	7/1/2015 to 7/30/2016	
Identification of PHCP, review of	Identification of PHCP, review of records,	7/1/2016 to 8/15/2017	
records, data entry-One year Follow up	data entry		
Data Management	Data entry, data cleaning, simple analysis	7/15/2015 to 10/15/2017	
Simple Results	Statistical analysis, interpretation	11/15/2017	
Presentation of Results	Abstracts writing, submission and presentation	11/15/2017 to 1/1/2018	
Manuscript	Writing of manuscript, submission	12/30/2017 to 3/31/2018	

L. Additional Information: Abbreviations glossary is provided below.

RA (Rheumatoid Arthritis); PHCP (Primary health care provider); EI (Educational intervention); CVD (Cardio-vascular disease); CVR (Cardiovascular risk); CAD (Coronary artery disease); CVRA (Cardiovascular risk awareness); CVRS (Cardiovascular risk screening);RUMC (Rush University Medical Center), JSH (John H Stroger Hospital); PI (Primary investigator); Co-I (Co investigator); NIH (National Institute of Health).

M. References:

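### Chart abstraction of cardiovascular risk screening (CVRS, Aim 2B) is not masked to group, although some checklist items need judgement and the review task can reveal the group

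*Protocol*

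**What the plan says.** All references are to the protocol.

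- **How CVRS is measured.** Section I.6: "Rates for CVRS at baseline and one year later for all RA patients (with and without EI) will be determined using a checklist". Section I.7, Aim 2B: "The medical records of RA patients with and without EI will be reviewed in electronic medical record, and analyzed using standardized checklist". Changes in CVRS rates are then compared between groups by chi square at a two-sided p of 0.05 or less.
- **What is scored.** The CVRS definition in section I.1 mixes factual entries (lipid panel, glycosylated hemoglobin) with items that need interpretation. One is "education on exercise in past one year". Others are smoking-cessation education and blood pressure control, for which no threshold is given. These three apply only to patients who have the risk factor.
- **Who obtains the records.** For outside providers, section I.2 says "we will contact their local PHCP to obtain their pertinent medical records to quantify prevalence of CVRS by PHCP". The abstractor is not named. Table 5 mentions "training of research assistant, study cordinator".
- **What the review task contains.** Table 5 describes it as "Identification of PHCP, review of records, data entry". Under the inclusion criteria, a PHCP must care for a recruited intervention patient and meet the condition "Not providing PHCP to RA patients in the" non-intervention group.
- **When.** Table 5 dates baseline review 7/1/2015 to 7/30/2016 and one-year review 7/1/2016 to 8/15/2017. A data management row, "Data entry, data cleaning, simple analysis", runs 7/15/2015 to 10/15/2017. Formal statistical analysis is dated 11/15/2017.
- **Expected direction.** Table 1 expects CVRS to be significantly higher at one year than at baseline in intervention patients.

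**The concern.** The protocol sets out the source, tool, timing and test for CVRS, but does not say that the abstractor is kept unaware of group. Masking of outcome assessment is a matter of study conduct and belongs in the protocol, so an unseen SAP would not settle it.

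An abstractor who knows the group, and knows the expected result, may credit a brief note on exercise or smoking more readily in an intervention chart. That would enter the between-group comparison as a treatment effect, and the planned chi-square and regression analyses could not separate it out.

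A second, lesser risk is drift. If items are credited more or less strictly in the second review period than in the first, the change over time within the intervention group is distorted.

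CVRS is the trial's only measure of whether greater awareness changes the care patients receive, so an ascertainment artefact here would be easy to misread.

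**Working it through.** **1. Can the abstractor learn the group?**

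- Table 5 puts PHCP identification and record review in one task.
- Enrolled PHCPs must treat intervention patients and must not treat non-intervention patients.
- An abstractor who identifies a PHCP and knows that this PHCP is enrolled can therefore infer that the patient is in the intervention group. The protocol does not withhold either piece of information.

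**2. Which items are exposed?**

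- Exposed: cessation education, exercise education, blood pressure control.
- Less exposed: lipid panel and glycosylated hemoglobin, which are factual. The obesity item can be met by a recorded BMI, so it is only partly a judgement.

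**3. Which comparison does each mechanism affect?**

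Write the recorded change in each group as true change plus common drift d, plus a group-specific crediting gap g in intervention charts at one year.

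- Within the intervention group: recorded change = true change + d + g.
- Between groups: (true change, intervention + d + g) − (true change, control + d) = true difference + g.

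Common drift cancels in the second line, at least approximately, while g does not. Drift therefore mainly threatens the Table 1 before-after expectation, and knowledge of group threatens the test in section I.7.

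**4. How large could the effect of g be?**

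The protocol gives no figure to reproduce, so this is an illustration.

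- Inputs from the protocol: 150 per group; two-sided 0.05.
- Assumed inputs: no true difference; recorded one-year rates of 45% and 55% (a 10-point gap around 50%); share of patients eligible for an item 30%, 50% or 100%, that is 45, 75 or 150 per group. The protocol gives no prevalence for the risk factors.

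Formulas, with n eligible per group and D = 0.10:

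- SE0 = √(2 × 0.5 × 0.5 / n)
- SE1 = √((0.45 × 0.55 + 0.55 × 0.45) / n)
- Rejection probability = Φ((D − 1.96 × SE0)/SE1) + Φ((−D − 1.96 × SE0)/SE1)

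| n per group | SE0 | SE1 | first term | second term | false-positive rate |
|---|---|---|---|---|---|
| 45 | 0.1054 | 0.1049 | Φ(−1.016) = 0.155 | 0.002 | about 16% |
| 75 | 0.0816 | 0.0812 | Φ(−0.739) = 0.230 | 0.001 | about 23% |
| 150 | 0.0577 | 0.0574 | Φ(−0.229) = 0.409 | below 0.001 | about 41% |

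Smaller assumed gaps give less. A 5-point gap gives about 7.6%, 9.4% and 13.9% for the three sizes, and a 3-point gap about 5.9%, 6.5% and 8.1%. The calculation compares one-year rates, whereas section I.7 compares changes, so it shows order of magnitude only.

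**The case against.** The strongest reply is that silence on masking is not a statement that abstractors are unmasked, and that the protocol never says the person showing the video also reads the charts. That is correct, and the point here is limited to a missing safeguard. The reply also notes that the checklist is described as standardized and that several items are factual. This stands and narrows the exposure to the judgement items.

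Three stronger readings are tempting and are not supported.

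- **That outcome data are being analysed by group while charts are abstracted.** A reader might infer this from the simple analysis listed under data management. Table 5 does not say that this work is by group, and it dates formal analysis 11/15/2017, three months after one-year abstraction ends on 8/15/2017. What remains is that nothing bars abstractors from seeing by-group awareness results in the meantime.
- **That drift between review periods biases the group comparison.** Drift common to both groups largely cancels there. It would not cancel if abstractors knew the group or if the groups were enrolled at different times. Two chart windows are inherent in a before-after outcome.
- **That the false-positive rate is 41%.** That needs a 10-point gap and all 150 patients per group eligible, while the judgement items apply only where the risk factor is present.

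It is also fair to say that CVRS is a secondary outcome of a pilot, that Aim 2B is worded as exploratory, and that the primary awareness outcome is untouched. This limits the weight of the point but does not remove it, because the comparison is still tested at 0.05.

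**Conclusion.** The point holds in a limited form. As written, CVRS is abstracted with some judgement items, no masking to group is provided for, and the review task itself offers a route to learning the group. Knowledge of group could bias the intervention versus non-intervention comparison of change in CVRS; drift is chiefly a threat to the before-after rise expected in Table 1.

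The size of any bias is unknown. The range of about 16% to 41% rests on an assumed 10-point crediting gap near 50%, on assumed eligibility of 30% to 100%, and on one-year rates in place of changes. That any staff member both delivers the video and abstracts the charts is an inference, since the abstractor is not named. The matter should be corrected because the remedy is cheap, but it does not endanger the primary outcome.

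**What to change.** Amend the CVRS text in sections I.2, I.6 and I.7 as follows.

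1. Name who abstracts. Use an existing staff member (research assistant or study coordinator) who did not show the video to that patient.
2. Give the abstractor a patient list without group or PHCP-enrolment status, and have the other staff member identify the PHCP and request outside records.
3. Write one crediting rule for each judgement item, including what counts as documented education and as blood pressure control, and apply the same rule at baseline and one year.
4. Release no by-group results to abstractors until one-year abstraction is closed.

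The cost is some reallocation of staff work and a few lines of text. Masking may be incomplete where the chart itself reveals the group, and the protocol should say so. Full de-identification of records, or reading both windows in one sitting after month 12, is not needed. The first means considerable extra work. The second shows the abstractor which window is which and shifts the baseline workload into the one-year review.
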